(d)Spinal Cord Injury Quality of Life Questionnaire (SCI QL-23): This is a routine test performed for people with spinal cord injury. The SCI QL-23 is a 23-item health-related quality of life questionnaire (weighted scale, aggregate score: GQOL: overall rating of life situation; FUNC: physical and social limitations; DEPR: distress and depressive feelings; PROB: perceived loss of independence and other issues relating to injury [Copyright © 1990 Health Care Research Unit, Sahlgrenska University Hospital, Sweden]). The subject will read the questionnaire and answer the questions; if needed ,assistance will be provided to record the answers on the form. The SCI QL-23 questionnaire will be used for all subjects.

(e)Veterans RAND 36-Item Health Survey (VR-36): This is a routine test performed for people with health related issues. The VR-36 is a health-related quality of life questionnaire (weighted scale, aggregate score [Copyright © Boston University School of Public Health, MA]. The subject will read the questionnaire and answer the questions; if needed, assistance will be provided to record the answers on the form. The VR-36 questionnaire will be used for all subjects.

(f)Functional Reach (FR) Test: This is a routine test performed for people with spinal cord injury. This test is used to evaluate trunk balance. This test is performed by patient reaching forward as far as they can while seated in their wheelchair. The distance traveled by the top of the reference shoulder is measured; 2 practice trials and 1 actual reach test is performed for the purpose of the study. The forward and lateral reach will be assessed on all subjects.

(g)Level of Trunk Activation: This is a routine test performed for people with spinal cord injury. This test will assess the activation of trunk muscle by asking the patient to perform a sit-up from the supine position. Using landmarks such as sterna angle, nipple line, supra-sternal notch, and ribs the lowest level of trunk activation will be determined. This test will be performed on all subjects.

(h)Grasp/Pinch Testing: This is a routine test performed for people with spinal cord injury. This is a standard test used to assess strength of grasp and lateral pinch. The Jamar dynamometer will be used to assess grasp and lateral pinch. This test will be performed on all subjects.

Version: 2
 Date: January 13th 2015
 Principal Investigator: [name].
Application Number: NA_00044093

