	2 hours	1 hours	10 minutes	2 hours	2 hours	10 minutes	10 minutes
Vital Signs	√			√	√		
PFTs	√			√	√		
ASIA	√			√	√		
SCI QL-23	√			√	√		
VR-36	√			√	√		
Functional Reach	√			√	√		
Trunk	√			√	√		
Grasp/Pinch	√			√	√		
Sailing Ability	√				√		
Cardio-Vascular		√					
Sailing Score		√					

Version: 2
 Date: January 13th 2015
 Principal Investigator: [name].
Application Number: NA_00044093

Diary				√				
Follow-up Q							√	√

Table 2: Data Collection Schedule

The following assessments will be performed at the Initial, and 12 Week visits:

- (a) Vital Signs (about 5 mins)
- (b) Pulmonary Function Test (about 5 mins)
- (c) ASIA (60 mins)
- (d) SCI QL-23 (about 10 mins)
- (e) VR-36 (about 10 mins)
- (f) Functional Reach Test (about 5 mins)
- (g) Level of Trunk Activation (about 5 mins)
- (h) Grasp/Pinch test (about 5 mins)
- (i) Sailing Ability Questionnaire (about 5 mins)

The following assessments will be performed at the 6 Week visits:

- (a) Vital Signs (about 5 mins)
- (b) Pulmonary Function Test (about 5 mins)
- (c) ASIA (60 mins)
- (d) SCI QL-23 (about 10 mins)
- (e) VR-36 (about 10 mins)
- (f) Functional Reach Test (about 5 mins)
- (g) Level of Trunk Activation (about 5 mins)
- (h) Grasp/Pinch test (about 5 mins)

The following assessments will be performed at all VSail training Visits:

- (j) Cardio-Vascular Monitoring (about additional 5 minutes to VSail session)
- (k) Sailing Score (about 5 minutes included in VSail session)

The following assessments will be performed weekly during the training:

- (l) Weekly Diary review (about 10 minutes), once a week only

The following assessments will be performed at the 6 Month and 12 Month visits:

- (m) Follow-up Questionnaire (about 10 mins)

c. Blinding, including justification for blinding or not blinding the trial, if applicable.

Not Applicable.

d. Justification of why participants will not receive routine care or will have current therapy stopped.

All subjects will continue to consistently perform their usual (“baseline”) amount of physical activity throughout the study, including clinic and home exercise program. “Baseline” activity is defined as amount of physical activity performed for at least 1 month prior to enrollment. Routine care will not be interrupted.

e. Justification for inclusion of a placebo or non-treatment group.

Not Applicable.

Version: 2
Date: January 13th 2015
Principal Investigator: [name].
Application Number: NA_00044093

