f. Definition of treatment failure or participant removal criteria.

Subjects may withdraw from the study at any time for any reason.

The subject may be removed from the study for any of the following reasons:

- a. The subject experiences a medical emergency that necessitates discontinuation of therapy
- b. The subject experiences a serious adverse event that is judged to be likely related to the therapy or is of severity that warrants discontinuation of treatment.
- c. For any medical reason at the discretion of the investigator.
- d. Subject is no compliant: participants who miss more than 3 sessions of training for the duration of the study.

g. Description of what happens to participants receiving therapy when study ends or if a participant's participation in the study ends prematurely.

Upon completion of the study, participants will be referred back to their treating SCI specialist who will be made aware of the treatment and follow-up. The same protocol will be followed for patients who terminate the study early. In the event of discontinuation due to adverse event, participants will be followed by the PI until resolution or stabilization of their adverse condition and then referred back to their treating SCI specialist.

Version: 2
Date: January 13th 2015
Principal Investigator: [name].
Application Number: NA_00044093

Inclusion/Exclusion Criteria

h. Inclusion:

- a. Males and Females, age 18-75, all ethnic groups.
- b. Spinal Cord Injury.
- c. Chronic injury, > 6 months from the injury.
- d. All ASIA neurological levels (C1-S1) as per Table 1.
- e. All ASIA impairment scale A-D as per Table 1.
- f. Subjects are able to comply with procedures and follow-up.
- g. Subjects are medically stable, with no recent (1 month or less) inpatient admission for acute medical or surgical issues.

i. Exclusion:

- a. Cardiovascular disease as defined by previous myocardial infarction, unstable angina, requirement for anti platelet agents, congestive heart failure, or stroke NYHA Class III or IV, history of arrhythmia with hemodynamic instability.
- b. Uncontrolled hypertension (resting systolic BP > 160mmHg, or diastolic BP > 100mmHg consistently).
- c. Severe hypotension (systolic BP < 80 mmHg, or diastolic BP < 55 mmHg).
- d. Ventilator dependant subjects.
- e. Significant cognitive impairment.
- f. History of epileptic seizures.
- g. Unstable long bone fractures of the extremities.
- h. Subjects having Stage III or greater skin ulcerations.

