d. Early stopping rules.

This is a pilot study. No early stopping rules have been set. Subject will be removed from the study as per treatment failure or removal criteria listed in section 3.f.

6. Risks

a. Medical risks, listing all procedures, their major and minor risks and expected frequency.

The medical risks are defined in the section below. This allows combining the risk and risk management in the same section for each risk.

b. Steps taken to minimize the risks.

All assessments and intervention sessions will be supervised by the Principal Investigator.

For all the study procedures, the risks and risk management are defined in the sections below.

(1) Intervention Risks:

VSail:

There is a minimal risk of pressure sores, and skin break down. **To further minimize the risk**, the subject seating in the VSail will be assessed and necessary precautions will be taken and proper protection equipment (gloves) will be used.

Version: 2
Date: January 13th 2015
Principal Investigator: [name].
Application Number: NA_00044093

There is a minimal risk of falls during transfers in/out of the VSail. **To minimize the risk**, subjects will be transferred using standard transfer procedures that are in use clinically at the ICSCI.

There is a minimal risk of fatigue, autonomic dysreflexia, or orthostatic hypotension. **To minimize the risk**, subjects are actively monitored during VSail training as described above (**(i) Cardio-Vascular Monitoring**), by a study team member trained in the procedure.

(2) Assessment Risks:

Vital Signs: There are no known risks associated with this measurement.

Pulmonary Function Test (PFTs): The risk is minimal for most people. Since the test involves some forced breathing and rapid breathing, patients may have some temporary shortness of breath or light-headedness. Patients breathe through a tight-fitting mouthpiece, and will have nose clips. To **minimize the risk**, a study team member trained in the procedure will perform the test.

ASIA test: There is a risk of discomfort at the site of the pin prick during the ASIA Exam. To **minimize the risk**, a study team member trained in the procedure will perform the ASIA exam.

Spinal Cord Injury Quality of Life Questionnaire (SCI QL-23): Aside from the risk associated with disclosing personnel or protected health information outside the research study, there are no known risks associated with this measurement.

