Veterans RAND 36-Item Health Survey (VR-36): Aside from the risk associated with disclosing personnel or protected health information outside the research study, there are no known risks associated with this measurement.

Functional Reach (FR) test: Patients may feel anxiety related to loss of balance. To **minimize the risk**, a study team member trained in the procedure will perform the test and will position themselves in the direction of the lean so subject does not fall.

Level of Trunk Activation: Patients may feel anxiety related to loss of balance. To **minimize the risk**, a study team member trained in the procedure will perform the test.

Grasp/Pinch Testing: There are no known risks associated with this measurement.

Sailing Ability Questionnaire: Aside from the risk associated with disclosing personnel or protected health information outside the research study, there are no known risks associated with this measurement.

Cardio-Vascular Monitoring: This is a vital signs measurement. There are no known risks associated with this measurement.

Sailing Score: There are no known risks associated with this measurement.

Weekly Diary: Aside from the risk associated with disclosing personnel or protected health information outside the research study, there are no known risks associated with this measurement.

Version: 2
Date: January 13th 2015
Principal Investigator: [name].
Application Number: NA_00044093

Follow-up Questionnaire: Aside from the risk associated with disclosing personnel or protected health information outside the research study, there are no known risks associated with this measurement.

(3) Other Risks:

Time Commitment: The time commitment for the training over the 12 weeks may be inconvenient, as well as the follow-up. **To minimize the risks:** 1] The subject will be asked to contact the study coordinator if having problems scheduling the visits; 2] If we feel that the subject can not commit the time and effort, he/she will be excluded from the study; 3] The visits may cause moderate social, school and work disruption. The start of the study will be scheduled to lessen those disruptions; 4] the follow-up questionnaire can be mailed to the subject or done over the phone.

c. Plan for reporting unanticipated problems or study deviations.

Adverse events, unanticipated problems and/or study deviations will be reported in writing by the Principal Investigator to the JHM-IRB and KKI Office of Research Compliance.

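### Missing more than 3 of 12 sessions can end study participation, with no outcome assessment stated afterwards, so week-12 and follow-up data may come selectively from better attenders

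*Protocol*

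**What the plan says.** All references are to the protocol.

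- **Section 3.f** opens permissively: "The subject may be removed from the study for any of the following reasons". Item d is non-compliance, defined as "participants who miss more than 3 sessions of training for the duration of the study". Training is one session a week for 12 weeks (3.a, 3.b), so the rule bites at the fourth miss.
- **Section 5.d** reads: "Subject will be removed from the study as per treatment failure or removal criteria listed in section 3.f".
- **Section 6.b.(3), Time Commitment**, adds: "If we feel that the subject can not commit the time and effort, he/she will be excluded from the study". It does not say whether this applies before or after enrolment.
- **Section 3.g** describes referral back to the treating specialist at completion, then states: "The same protocol will be followed for patients who terminate the study early". After an adverse event it adds follow-up until the condition resolves or stabilises. It mentions no outcome assessment after early termination, but it does not say that assessments stop.
- **Section 3.a.(2)** says of the two quality-of-life surveys: "The SCI QL-23 questionnaire will be used for all subjects" and "The VR-36 questionnaire will be used for all subjects".
- **Section 3.b** introduces the main battery, which includes both surveys, with "The following assessments will be performed at the Initial, and 12 Week visits". The 6- and 12-month contacts consist of the Follow-up Questionnaire.

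**The concern.** Removal is worded as leaving the study. Nowhere does the protocol describe a subject who stops the simulator sessions but still attends for assessment. If the rule is applied, a subject with four or more misses gives no data from that point on, and whether week-12 data exist depends on attendance.

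The data at stake are:

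- the week-12 SCI QL-23 and VR-36, which serve primary outcome 2 (section 5.a);
- the six week-12 physical tests (vital signs, pulmonary function, ASIA, functional reach, trunk activation, grasp/pinch), which supply all four secondary outcomes (section 5.b);
- the Sailing Ability Questionnaire, which Table 2 schedules only at baseline and week 12, so a removed subject would have no later value at all;
- the 6- and 12-month Follow-up Questionnaire.

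The last two are not listed outcomes. The Sailing Score is taken only at training visits and would end with training in any case, so it is not part of this point.

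The study has one group, measured before and after. The week-12 surveys and tests are its end-of-course evidence for Hypothesis 2. If they are missing mainly in poor attenders, the observed change describes better attenders.

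**Working it through.** **Inputs from the protocol.** There are 20 subjects (Table 1: 5 injury levels × 2 completeness groups × 2 per cell = 20, which reproduces the stated enrolment) and 12 sessions. The threshold is 4 or more misses, so anyone retained under a strictly applied rule attended at least 9 of 12. The protocol gives no attendance or dropout rate. Every miss rate below is an assumption.

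**1. How many subjects could be affected?** Let p be the chance of missing a session.

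- Independent misses: q = P(Bin(12, p) ≥ 4). The expected number is 20q, and the chance of at least one is 1 − (1 − q)^20.
- Misses clustered within subjects: beta-binomial with assumed intra-subject correlation 0.2, that is a = 4p and b = 4(1 − p).

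| Assumed p | q, independent | Expected of 20 | P(at least one) | q, clustered | Expected of 20 |
|---|---|---|---|---|---|
| 5% | 0.0022 | 0.04 | 4% | 0.0501 | 1.0 |
| 10% | 0.0256 | 0.5 | 40% | 0.1148 | 2.3 |
| 15% | 0.0922 | 1.8 | 86% | 0.1908 | 3.8 |
| 20% | 0.2054 | 4.1 | 99% | 0.2747 | 5.5 |
| 25% | 0.3512 | 7.0 | nearly 100% | 0.3626 | 7.3 |

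**2. Would week-6 data exist?** Among subjects who reach four misses, the share who do so within the first six sessions is P(≥ 4 of 6) / P(≥ 4 of 12). For p from 10% to 25% this is 0.050 to 0.107 under independence and 0.242 to 0.328 under clustering. So week-6 values could exist for 89–95% or 67–76% of them. Week-6 data usually survive; week-12 data do not.

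**3. Effect on the mean change.** Let k of 20 subjects have no week-12 value, and let D be the mean change in attenders minus the mean change that removed subjects would have shown.

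- Observed mean = M_att.
- All-subject mean = [(20 − k)·M_att + k·M_rem] / 20.
- Difference = (k/20)·(M_att − M_rem) = (k/20)·D.

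For an assumed D of ±0.5 SD, with the standard error of the mean change equal to 1/√(20 − k) in SD units:

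| k | Shift (SD) | Standard error (SD) | Shift / standard error |
|---|---|---|---|
| 1 | ±0.025 | 0.229 | 0.11 |
| 4 | ±0.100 | 0.250 | 0.40 |
| 7 | ±0.175 | 0.277 | 0.63 |

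D is unknown. It is zero if removed subjects would have changed equally, and its sign depends on why sessions were missed.

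**4. The wordings side by side.** 3.f permits removal. 5.d says it will happen, but by reference to 3.f, so it can be read either as mandatory or as carrying over the permission. 6.b.(3) says exclusion will follow a judgement about commitment. None of the three separates stopping the sessions from leaving the study.

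**The case against.** The strongest case against is about weight.

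- **The conflict in wording is soft.** 5.d is a cross-reference, and its natural reading imports the permission in 3.f. The 6.b.(3) sentence sits among measures against inconvenience and need not concern missed sessions. This stands: the wordings are ambiguous rather than flatly contradictory, but site staff must still choose a reading without guidance.
- **The statement that a survey is used for all subjects is not a retention promise.** The phrase closes most assessment descriptions and means only that the test is not limited to a subgroup. This also stands, and the point does not depend on it.
- **Better attenders may be the right group.** Section 1 words Hypothesis 2 around people who have learned to sail to a level of competence. The opening summary puts it more broadly, as the effect of teaching patients to sail. This limits the concern but does not remove it.
- **It is a pilot with no planned statistical analysis (5.c).** A descriptive summary is affected by selective collection just as a test is, and 3.a says the pilot is to give preliminary evidence on both hypotheses.
- **The effect may be negligible.** Subjects are already in rehabilitation and must be able to comply (inclusion criterion f), so low miss rates are plausible. At 5% the expected number is 0.04 under independence and about 1.0 under clustering. Even the larger illustrations stay below one standard error. This stands.
- **The protocol is silent rather than wrong.** 3.g does not say that assessments stop, and an investigator may keep a poor attender under 3.f. That is true, but applying the stated rule as written loses the data, and what is collected after training stops is a protocol matter that an analysis plan cannot repair.

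**Conclusion.** The concern holds as a worthwhile improvement, not as a defect that invalidates the pilot. The protocol allows, and in 5.d can be read as requiring, removal from the study for poor attendance, and it states no outcome assessment afterwards. If applied, the rule makes the week-12 evidence on primary outcome 2 and all secondary outcomes, and the later questionnaires, depend on attendance.

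The number affected cannot be derived from the document: the illustrations run from almost none to about 7 of 20. The resulting shift in mean change is modest, of unknown sign and possibly zero. Week-6 values would usually be available and may help, but they do not replace end-of-course values. Confidence is medium, because the consequence depends on an unknown attendance rate and on how the permissive wording would be used.

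**What to change.** 1. Reconcile the removal statements in 3.f, 5.d and 6.b.(3), and say whether the last applies before or after enrolment.
2. In 3.f and 3.g, distinguish stopping the simulator sessions from withdrawing from the study.
3. State that, unless consent is withdrawn and where medically possible, a subject who stops sessions keeps the already scheduled week-6 and week-12 assessments. Keep the 6- and 12-month questionnaires too, by the mail or telephone route that 6.b.(3) already allows.

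No view is taken on the attendance threshold, on which removal wording is right, or on the clinical reasons for stopping.

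The cost is protocol wording plus, per non-attender, one visit that was already planned and two 10-minute questionnaires. The week-12 assessments listed in 3.b total 5 + 5 + 60 + 10 + 10 + 5 + 5 + 5 + 5 = 110 minutes, of which the two quality-of-life surveys take 20. Some subjects will decline, so the loss is reduced rather than removed.
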